## 1.3 Follow-Up

Part 1 was terminated early after an interim analysis of a phase 3 study in infants with SMA (ISIS 396443-CS3B) demonstrated a positive benefit-risk profile for Nusinersen. Subjects returned to the study site for a follow-up evaluation (Final Study Visit) approximately 4 months after the last dose of study treatment in Part 1 and all eligible were enrolled in Part 2. Part 2 will terminate early as well to allow subjects to enroll in another long term Phase 3 open-label extension study, ISIS 396443-CS11. Subjects who terminate early from Part 2 of the study will be encouraged to complete the Part 2 Early Termination Evaluation assessments at the time of withdrawal.

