#### *Integrated analysis*

The HINE motor milestones, growth parameters and CGI, laboratory data, CSF and Plasma concentrations integrated analyses will be windowed as follows:

Study days  $\leq 1$  will be labelled Baseline

- Study days  $> 1$  to  $\leq 22$  will be labelled Day 15
- Study days  $> 22$  to  $\leq 47$  will be labelled Day 29
- Study days  $> 47$  to  $\leq 123$  will be labelled Day 64
- Study days  $> 123$  to  $\leq 242$  will be labelled Day 183
- Study days  $> 242$  to  $\leq 362$  will be labelled Day 302
- Study days  $> 362$  to  $\leq 482$  will be labelled Day 422
- Study days  $> 482$  to  $\leq 600$  will be labelled Day 540
- Study days  $> 600$  to  $\leq 719$  will be labelled Day 659
- Study days  $> 719$  to  $\leq 838$  will be labelled Day 778
- Study days  $> 838$  to  $\leq 958$  will be labelled Day 898
- Study days  $> 958$  to  $\leq 1078$  will be labelled Day 1018
- Study days  $> 1078$  to  $\leq 1198$  will be labelled Day 1138

If multiple results are allocated into the same window then the closest non-missing result to the target date will be chosen.

In order to account for the denominator across the analysis visits, an Efficacy set for each windowed analysis visit (Day X) will be defined as: a subset of subjects in the Safety set who have the opportunity to be assessed at the Day X visit, where the lower bound for the windowed analysis visit are denoted: L= lower. Specifically, it will include all subjects with a time difference of at

least L days between the date of first dose and the end of Part 2. A subject who has died or withdrawn will be included provided that there is a difference of at least L days between the date of first dose and the end of Part 2. In a situation where the subject was known to have withdrawn from the study at a date within the window due to rolling over to commercial drug then they will be excluded from the corresponding Efficacy set and subsequent analysis visit Efficacy sets.

An evaluable set will be defined for each analysis visit as the subset of subjects in the Efficacy set at the analysis visit who meet the following criteria:

- Value assigned from the windowing
- Subject who died or discontinued from the study – no imputation of efficacy data will be performed for such subjects and they will be considered non-responders.

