- No value assigned from windowing, but ongoing in study with a subsequent assessment assigned to a later analysis visit. In this situation, a value will be imputed as the value from the analysis visit prior to the missing visit.

A couple of considerations as part of this final criterion are as follows:

- In a situation where a subject does not have a windowed value at analysis visit X and is known to discontinue at the next visit, X+1, without an efficacy assessment, the subject would not be included within the denominator for the responder analysis at visit X, but they would be included as a non-responder at visit X+1.
- In a situation where a subject does not have a windowed value at analysis visit X and is known to discontinue at the next visit, X+1, with an efficacy assessment prior to the discontinuation, the subject would be included within the denominator for the responder analysis at visit X and the last observed value will be utilized, and then they would be included as a non-responder at visit X+1.

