#### 4.5.1 HINE motor milestones

HINE Section 2 comprises eight tests for motor milestones: head control, sitting, voluntary grasp, ability to kick in supine position, rolling, crawling, standing, and walking.

There are 26 possible motor milestones that can be achieved using this schema (presented below). A subject whose results all appear in the first column (unable to maintain head upright, cannot sit, no grasp, etc.) has not achieved any motor milestone. A subject whose results all appear in the second column (head wobbles, sits with support at hips, uses the whole hand for a voluntary grasp, etc.) has achieved 8 motor milestones. A subject whose results all appear in the third column (head maintained upright all the time, props when sitting, index finger and thumb but immature grasp, etc.) has achieved 16 motor milestones.

*Attainment of motor milestones assessed by Section 2 of the Hammersmith Infant Neurological Examination (HINE)*

For the integrated analysis, the HINE motor milestones analyses will be presented by windowed analysis visits (see section 4.1).

The definition of a motor milestone responder is based upon the motor milestones categories in Section 2 of the HINE, with the exclusion of voluntary grasp as follows:

- Subject demonstrates at least a 2-point increase in the category of ability to kick or increase to the maximal score on that category (touching toes), or a 1-point increase in the motor milestones category of head control, rolling, sitting, crawling, standing, or walking AND
- Among the motor milestone categories, with the exclusion of voluntary grasp, there are more categories where there is improvement, as defined in (i) below, than there are categories where there is worsening (as defined below).
- Subjects who die or withdraw from the study on or prior to the visit will be counted as non-responders and will be included in the denominator

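### A child who leaves for commercial drug is removed from the whole visit window of exit, so a HINE already done in that window drops out of the integrated by-visit analyses

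*SAP*

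**What the plan says.** SAP 4.1 (Visit Windowing, Integrated analysis) assigns results to windows around target days. Within a window, "If multiple results are allocated into the same window then the closest non-missing result to the target date will be chosen". Each window has an Efficacy set, which SAP Section 2 describes as the children who had the opportunity to be assessed at that visit.

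Commercial roll-over has its own rule. The trigger is stated as "In a situation where the subject was known to have withdrawn from the study at a date within the window due to" roll-over, and the consequence is exclusion from that window and from every later one ("rolling over to commercial drug then they will be excluded from the corresponding Efficacy set and subsequent analysis visit Efficacy sets"). The trigger is the exit date. Nothing is said about a child who already has a value in the window.

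The evaluable set is then built inside the Efficacy set: "An evaluable set will be defined for each analysis visit as the subset of subjects in the Efficacy set at the analysis visit" who meet further criteria, one of which is having a value assigned by the windowing.

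Other leavers are treated differently:

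- In SAP 4.1, for children who died or discontinued, "no imputation of efficacy data will be performed for such subjects and they will be considered non-responders".
- Also in SAP 4.1, for a child with no value at visit X who is assessed before discontinuing at X+1, "the last observed value will be utilized, and then they would be included as a non-responder at visit X+1".
- In SAP 4.5.1 (HINE motor milestones): "Subjects who die or withdraw from the study on or prior to the visit will be counted as non-responders", and they stay in the denominator. No commercial-drug exception is given there.

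On the exit visit, SAP 1.3 says: "Subjects who terminate early from Part 2 of the study will be encouraged to complete the Part 2 Early Termination Evaluation assessments". The Part 2 schedule tables mark HINE in that column.

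**The concern.** Excluding a child from windows after a move to commercial drug is reasonable, because the child can no longer be examined in the study. Excluding the child from the window of exit is harder to defend when the examination in that window was done while the child was still on study drug. Such a child had the opportunity to be assessed and was assessed, so removal goes against the SAP's own principle for the Efficacy set.

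The planned groups are at most 14 and 7 children, so each valid value removed costs precision. If commercial leavers respond at a different rate from those who stay, the by-visit response rate also shifts. In addition, SAP 4.1 and SAP 4.5.1 give different answers for the same child, and a programmer would have to choose between them.

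**Working it through.** The plan gives no power calculation, no expected response rate and no count of commercial leavers, so there is no figure of its own to reproduce. The check has three parts.

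**1. Can an in-window value survive?** The order of sets is Safety set, Efficacy set, evaluable set, by-visit denominator. The commercial-drug rule acts at the Efficacy set. The criterion of having a windowed value acts one level lower, inside that set, so it cannot bring the child back. The SAP does not say in words that an observed value is dropped; this follows from an unconditional rule and nested sets.

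Example: a child examined on Day 540 leaves on Day 590. The Day 540 window covers study days 483 to 600, which is 600 - 482 = 118 days. Both dates lie in it.

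- Under SAP 4.1 the child is out of the Day 540 window and all later ones.
- Under SAP 4.5.1, read literally, withdrawal on Day 590 comes after a visit on Day 540, so the observed value would count at Day 540. In every later window the child would be a non-responder in the denominator.
- A HINE done on the withdrawal day itself could meet the SAP 4.5.1 non-responder rule in the exit window too.

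**2. How often would a value already exist?** Windows from Day 183 onward are 118 to 120 days long, with one scheduled HINE near the middle. Assume that exit dates are spread evenly over the window. For the previous-nusinersen group, assume also that Part 2 Day 1 falls on study Day 422, so that a Part 2 day d becomes study day 422 + d - 1.

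- Day 183 window (124 to 242): exits on Days 183 to 242 are 60 of 119, or 50.4%.
- Day 540 window, previous control (HINE on Day 540): exits on Days 540 to 600 are 61 of 118, or 51.7%.
- Day 1138 window, previous nusinersen (HINE on Day 422 + 715 - 1 = 1136): exits on Days 1136 to 1198 are 63 of 120, or 52.5%.

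Across the windows from Day 183 the share is 50% to 53%. In the Day 64 window (48 to 123) it is 60 of 76, or 79%. If a HINE is also done at the early termination visit, nearly every commercial leaver would have an in-window value.

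**3. What can it do to a response rate?** Let n be the children in the group at the window, k the commercial leavers with an in-window value, r the responders among the n - k stayers, and j the responders among the leavers.

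- Excluded (SAP 4.1): r/(n - k)
- Observed values used: (r + j)/n
- Difference, observed minus excluded: (k/n) × [j/k - r/(n - k)]

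The sign depends only on whether leavers respond better or worse than stayers. The difference cannot exceed k/n either way. With the planned 14 and 7 (protocol synopsis, up to 21 children randomized 2:1):

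| k (assumed) | n = 14 | n = 7 |
|---|---|---|
| 1 | ±7.1 points | ±14.3 points |
| 2 | ±14.3 points | ±28.6 points |
| 3 | ±21.4 points | ±42.9 points |

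Example with assumed counts: n = 14, k = 2, 6 of 12 stayers responding.

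- Excluded: 6/12 = 50.0%
- Observed, neither leaver responding: 6/14 = 42.9%
- Observed, both leavers responding: 8/14 = 57.1%
- Leavers counted as non-responders: 6/14 = 42.9%

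**The case against.** The strongest reply is that the rule may rarely or never apply. The documents give no count of commercial leavers. SAP Section 1 has all children ending Part 2 early to enter ISIS 396443-CS11, and protocol version 4 no longer carries the wording of versions 2 and 3 that ended Part 2 treatment when commercial product became available. The commercial-drug sentence reads as a contingency. This stands as a limit on size. It is not a reason to leave the rule as it is: protocol 5.2 records approval in the United States and Europe, and the SAP itself provides for such exits.

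Second, the value is not lost altogether. It may still enter the SAP 4.5.1 presentations at last available assessment (responder status, selected milestones, shift from baseline), and the Part 2-only analysis has its own relabelling rule. This stands: the loss is confined to integrated by-visit analyses that take their denominator from the Efficacy set.

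Third, an exit HINE is not assured. The visit is only encouraged, and a footnote to the schedule speaks of safety evaluations, whereas protocol 13.1 lists HINE under efficacy. This also stands, so the 50% to 53% for scheduled examinations is the safer figure.

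Fourth, other leavers may lose observed values too, since SAP 4.1 makes a child assessed before discontinuing at X+1 a non-responder at X+1. Crediting in-window values to commercial leavers alone would create a new imbalance. This is right, and the change has to cover all leavers who were assessed.

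**Conclusion.** The point holds as a minor one. The rule discards valid on-treatment results from the integrated by-visit analyses when the child was assessed in the exit window before moving to commercial drug. Each such child can move a response rate by up to 7.1 points at n = 14 or 14.3 points at n = 7. These are bounds at the planned sizes; smaller numbers under observation would raise them. The counts in the example are assumptions.

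A reader might infer that the rule biases response downwards, because families who move to commercial nusinersen have presumably seen benefit. The documents do not support that. They give no response data for these children, and children who enter ISIS 396443-CS11 also continue nusinersen, so choosing to continue does not mark out commercial leavers. If leavers respond worse than stayers, exclusion raises the rate, as the 42.9% end of the example shows. Compared with counting leavers as non-responders, exclusion can only leave the rate unchanged or raise it.

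Severity is limited because SAP Section 4 labels efficacy exploratory, the primary endpoints are safety, and the sample size rests on feasibility.

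**What to change.** Amend SAP 4.1 (Integrated analysis) along these lines: *A subject who rolls over to commercial drug remains in the Efficacy set of the window containing the roll-over date if an assessment on or before that date falls in the window, and that observed value is used. The subject is excluded from that window only if there is no such assessment, and is excluded from all later windows.*

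Then make two alignments:

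- In SAP 4.1 (the evaluable-set criteria and the considerations that follow them) and SAP 4.5.1, state that an assessment made in the exit window on or before withdrawal is handled the same way for every leaver who was assessed, whatever the reason for leaving.
- In the SAP 4.5.1 non-responder rule, add the commercial-drug exception for later windows, so that the two sections give the same denominator.

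The cost is a few lines of SAP text and minor reprogramming. No new data are needed.

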## 4.2 Ventilation data

Ventilator use during the study will be tracked at study visits, with details collected using a ventilation diary or other available sources. Caregivers will initiate collecting ventilation diary data for all subjects. Note, once the first entry of ventilation use has been recorded on the diary, then the diary will then need to be completed until the end of the study. If the daily number of hours of ventilation and the type is the same for consecutive days, then the first and last day date will be captured, together with the daily hours and type of ventilation – invasive/non-invasive (for prophylaxis or treatment). For days on which ventilator use was not recorded, the number of hours of use will be imputed using the greater of the daily values among the days that flank the missing day(s).

#### 4.2.1 Change in Ventilator use

In the statistical analysis of Part 1, for each subject the mean number of hours of ventilator was calculated amongst the periods. These periods were created from the first dose of Nusinersen or sham procedure to the nominal visit. (example Day 1: > from Day 1 to Day 15 visit; Day 15: from Day 15 inclusive to Day 29 visit). In Part 2 for each subject the mean number of hours will be calculated for a monthly interval (30 days) starting from the first dose of Nusinersen or sham procedure. The intervals will be: month 1 from Day 1 inclusive to Day 30, Month 2 from Day 30 inclusive to Day 60, and so on.

The change from baseline over time will be presented and a plot of both total and change from baseline will be presented.

For each subject, the total number of hours of ventilation support required during the study will be calculated and prorated according to number of days on study. The percentage of time on ventilator support in total and by type either invasive prophylactic, invasive treatment, or non-invasive prophylactic and not invasive treatment will be presented.

The different respiratory aids/therapies used will be listed

#### 4.2.2 Time to Death or Permanent Ventilation

Permanent ventilation is defined as tracheostomy or  $\geq 16$  hours of ventilatory support per day continuously for  $> 21$  days in the absence of an acute reversible event. This endpoint was not pre-specified in the protocol.

Time to permanent ventilation and acute reversible events will be determined by medical review. For all time-to-event endpoints (e.g., time to death or permanent ventilation), the date of first dose/sham administration will be used as the reference time point. If the date of first dose/sham procedure is incomplete, the date of randomization will be used. Only events that were adjudicated will be included in the analysis. Subjects who do not meet the endpoint definition will be censored at the last occasion the subject was seen (either in-person visit or by telephone contact), irrespective of whether the subject has completed a full course of treatment and whether the subject has completed the study or withdrawn prematurely. However, in the event that a subject has begun a ventilation diary, the latest entry in the diary will be used as the date of censoring. Of note, once a ventilation diary has been started, the diary will then need to be completed every day until the end of the study.

The median times to death or permanent ventilation and associated 95% confidence limits will be estimated using the Kaplan-Meier method. The proportion of subjects who meet such an event will be estimated from the Kaplan-Meier curve.

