¹ A blood sample will be collected at Screening for *SMN2* copy number only from those subjects without genetic documentation of *SMN2* copy number. For all other subjects, a blood sample will be collected at any time during the study for analysis of *SMN2* copy number by the central laboratory.

² After the injection of study treatment or sham procedure on Day 1, subjects will remain at the study site for at least 24 hours (Day 2) for safety monitoring. On the day following the injection of study treatment or sham procedure on Days 15, 29, 64, 183, and 302, there will be safety monitoring through telephone contact. During that telephone contact (i.e., Days 16, 30, 65, 184 and 303), changes in concomitant medications and AEs, information on the subject’s daily ventilator/Bi-PAP use, and health status will be recorded.

³ End of Part 1 is one of the following: Part 1 Final Follow-up Evaluation (Day 422 [±7 days]) according to the study schedule, early Part 1 Final Follow-up Evaluation to allow for rollover into Part 2, or Early Termination Evaluation for subjects who withdraw from the study during Part 1.

⁴ For subjects not transitioning into Part 2, the date of the End of Part 1 Evaluation assessments will be the end of study. For subjects who transition to Part 2, the date of the End of Part 1 will be the date of first dose in Part 2.

⁵ At the End of Part 1 evaluation, in order to allow transition to Part 2, subjects will be unblinded.

⁶ Vital signs include resting systolic and diastolic blood pressure, pulse rate, respiratory rate, temperature, pulse oximetry, and transcutaneous carbon dioxide. Pulse oximetry and transcutaneous carbon dioxide will be measured predose at each evaluation. For subjects who are not receiving noninvasive ventilation, pulse oximetry will be measured overnight once a week at home.

⁷ Vital signs (resting systolic and diastolic blood pressure, pulse rate, respiratory rate, temperature, and pulse oximetry) will be collected at 4 timepoints: 1, 2, 4, and 6 hours (all ±15 minutes) after the injection of study treatment.

⁸ Vital signs (resting systolic and diastolic blood pressure, pulse rate, respiratory rate, temperature, and pulse oximetry) will be collected within 20 to 24 hours after the injection of study treatment or sham procedure.

CONFIDENTIAL

The information contained herein may not be used, disclosed, or published without the written consent of Biogen MA Inc.

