7.2.2. Treatment

Part 1

Eligible subjects will be admitted to the study site on Part 1 Day 1, undergo predose evaluations, and then receive an LP injection of Nusinersen or a sham procedure. After the injection on Day 1, subjects will remain at the study site for at least 24 hours after the procedure for safety monitoring.

Subjects will return to the study site on Days 15, 29, 64, 183, and 302 (± 1 day for Days 15 and 29 and ± 7 days for all other days) for follow-up evaluations and subsequent injections of study treatment or sham procedure, for a total of 6 injections or sham procedures over a dosing period of 10 months. During these 5 evaluations, all subjects will remain at the study site for at least 6 hours postdose for safety monitoring. An overnight stay is optional, at the discretion of the Investigator. Safety monitoring by telephone contact will occur on the day after injection of study treatment or sham procedure. In addition, the study site will monitor the subject's condition through telephone contact every other week (excluding weeks with study visit) throughout the study period.

After completing the End of Part 1 Evaluation assessments, all eligible subjects may elect to enroll in Part 2.

Based on emergent data from the Nusinersen clinical development program, the Sponsor may decide to terminate Part 1 early, and all subjects may be offered the opportunity to transition to Part 2 prior to completion of all Part 1 Evaluation assessments. All subjects enrolled in the study at the time of Sponsor termination will be considered Part 1 completers. The next study evaluation for those subjects will serve as an End of Part 1 Evaluation, which may occur at any time prior to the next scheduled Part 1 study evaluation.

Unblinding will occur in order for the subjects to transition from Part 1 to Part 2.

End of Part 1 Evaluation assessments are required to be done prior to the transition to Part 2. After performing the End of Part 1 Evaluation assessments, the subject may immediately transition to Part 2.

Part 2

Part 2 study procedures and schedules will be determined based on the subject's treatment assignment in Part 1.

CONFIDENTIAL

The information contained herein may not be used, disclosed, or published without the written consent of Biogen MA Inc.

Subjects who were randomized to receive Nusinersen in Part 1

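### If a ventilation diary stops early, the censoring rule for death or permanent ventilation drops documented event-free time but keeps later events

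*SAP*

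**What the plan says.** SAP 4.2.2 counts a tracheostomy as permanent ventilation. It also counts 16 or more hours of support a day for over 21 days running, acute reversible events aside. It notes that the endpoint was not in the protocol and estimates it by Kaplan-Meier. The rules that matter here are:

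- Scope: "Subjects who do not meet the endpoint definition will be censored", so the censoring rule covers event-free children only.
- Default date: such children are "censored at the last occasion the subject was seen (either in-person visit or by telephone contact".
- Override: if a diary has been begun, "the latest entry in the diary will be used as the date of censoring".
- Events: "Only events that were adjudicated will be included in the analysis". No limit tied to the diary is stated.
- Diary duty: "once a ventilation diary has been started, the diary will then need to be completed every day until the end of the study".

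SAP 4.2 has caregivers start diary data for every child, with continued completion required after the first ventilation entry. It also takes ventilator use from visits and other sources, and fills unrecorded days from the larger of the neighbouring values. SAP 3.3 defines the last date on study from all available data, including visits and calls. SAP 4.2.3 (survival) gives no censoring rule of its own.

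In the protocol, sites follow the child's condition "through telephone contact every other week (excluding weeks with study visit) throughout the study period" (7.2.2). On the calls made the day after dosing, "daily ventilator/Bi-PAP use, and health status will be recorded" (4.2).

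**The concern.** The override replaces last contact instead of extending it. A child whose diary ends on one date but who is later documented alive and not permanently ventilated is still censored at the diary date. A child whose diary ends on the same date and who later dies is an event at the date of death. Event-free time after the last entry is removed from the risk set while events after it stay in, and that pushes the Kaplan-Meier risk upward. With at most 14 and 7 children randomized to the two arms, each child removed early changes the estimate visibly. The rule also departs from the last date on study that the SAP uses for exposure.

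**Working it through.** The plan states no event count, event rate or power for this endpoint, so there is no figure to reproduce. Two checks follow.

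**Hand example.** Kaplan-Meier risk = 1 − Π(1 − d/n), where d is the number of events and n the number at risk at each event time.

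- 7 children, one event on Day 250, all others seen beyond it: 1 − 6/7 = 14.3%.
- Same data, but two event-free children have diaries ending on Day 120. They leave the risk set, so n = 5: 1 − 4/5 = 20.0%.
- 14 children, deaths on Days 250 and 350, 12 event-free to Day 422: 1 − (13/14)(12/13) = 2/14 = 14.3%. With 3 event-free diaries ending on Day 200: 2/11 = 18.2%. With 6: 2/8 = 25.0%.

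**Simulation.** It used 14 children, exponential event times, follow-up to Day 422 (the scheduled Part 1 final visit) and 4,000 runs per setting. Diaries lapse at a uniform time, unrelated to prognosis. The following are assumptions, not document figures: the true risk, the share of children whose diary lapses, and the share of post-lapse events that can be detected without the diary. The last three columns are mean estimated risk.

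| True risk | Diaries lapsing | Later events detectable | SAP rule | Last contact | Events and censoring both cut at diary end |
|---|---|---|---|---|---|
| 15% | 0% | all | 0.149 | 0.149 | 0.149 |
| 15% | 10% | all | 0.159 | 0.152 | 0.152 |
| 15% | 25% | all | 0.169 | 0.149 | 0.149 |
| 15% | 50% | all | 0.200 | 0.151 | 0.151 |
| 15% | 25% | half | 0.162 | 0.142 | 0.151 |
| 15% | 25% | none | 0.150 | 0.132 | 0.150 |
| 15% | 50% | none | 0.151 | 0.115 | 0.151 |
| 30% | 25% | all | 0.332 | 0.300 | 0.299 |
| 30% | 25% | half | 0.316 | 0.282 | 0.301 |
| 30% | 25% | none | 0.301 | 0.267 | 0.301 |

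Three results follow. Without lapse, the three rules agree. With lapse, the SAP rule is too high to the extent that later events are still detected, and last-contact censoring is too low to the extent that they are not. Cutting events and censoring at the same date is unbiased in every setting, provided lapse is unrelated to prognosis.

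**The case against.** The strongest reply is the diary duty in the same paragraph. If the diary is kept daily to study end, the last entry falls at about the end of follow-up and nothing is lost. Gaps between entries do not trigger the problem either, because SAP 4.2 imputes them. This stands: only a diary abandoned before later contacts matters, and no document says that this happened. It does not remove the point. The SAP itself expects unrecorded days, and its imputation needs an entry on both sides, so it cannot repair a diary that has stopped.

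The second reply is that daily hours are needed to rule out the 16-hour, 21-day component, so the last entry is a reasonable limit. This also stands in part. A reader might infer that any later contact proves a child event-free, since contact alone is accepted for children without a diary. The documents do not support that for a child already on ventilation. Ventilator use is specified for the day-after-dose calls, which come 119 days apart after Day 65 (Days 65, 184, 303). For the fortnightly calls, the current Protocol 7.2.2 mentions only the child's condition. The reply is weaker for death, which must be reported (Protocol 15.3.3.1), and for tracheostomy, since surgical interventions are recorded as concomitant procedures (Protocol 11.5.2). And if the diary end is the intended limit of knowledge, it should limit events too.

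Third, the endpoint is exploratory, and SAP 4.2.2 plans no between-group test. That limits the consequence.

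**Conclusion.** As written, the rule is asymmetric and can overstate Kaplan-Meier risk. This requires a diary that stops before later contacts and later events that are known from other sources. The size is not determined by the documents. In the simulation, at a true risk of 15%, a quarter of diaries lapsing gives 16.9% if all later events are detected, 16.2% if half are, and 15.0% if none are. The Day 422 horizon is also a simplification, because Part 1 stopped early and sham children left first.

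Two stronger readings are tempting. One is that risk is in fact overstated among ventilated children. Neither part is established: no lapse rate is given, diaries are started for all children, and the SAP does not define when one counts as begun. The other is that the rule favours nusinersen. That needs more early-stopping diaries in the sham group, and nothing in the documents shows this.

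SAP 4.2.3 contains no diary rule, so it shows no error. It only needs to say that the override does not carry over. This is a minor point: a cheap improvement to an exploratory analysis.

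**What to change.** In SAP 4.2.2, replace the override as follows. Censor event-free children at the later of (a) the last diary entry and (b) the last visit or call at which the child was documented alive, without tracheostomy, and with ventilator use since the last entry ascertained as not meeting the permanent-ventilation definition. State when a diary counts as begun, and report diaries that end before last contact.

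As a sensitivity analysis, cut both events and censoring at the diary end. This covers the case that the main rule cannot: where hours after the diary cannot be recovered, (b) adds nothing and a later death would still count.

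In SAP 4.2.3, state that the diary override does not apply and that survival is censored at the last date known alive.

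The cost is a few sentences, one derived censoring date and one extra table. The downside is that, after a diary stops, ventilation status rests on visit or telephone report.
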